# Synopsis

## Primary Objective

To compare patient-reported outcomes of insomnia collected through Hugo, as well as clinically validated metrics for insomnia among patients randomized to receive the Prescription Digital Therapeutic (PDT) + Fitbit vs. Fitbit only at 9, 21, 35, and 61 weeks post-randomization.

## Secondary Objective

**Secondary Objectives:** (1) To compare real-world healthcare utilization/clinical data collected through Hugo, including number of outpatient visits with primary care physicians, number of outpatient visits with specialty care, and medication refills for sleep or psychotropic medications among patients randomized to receive PDT + Fitbit vs. Fitbit only at 9, 21, 35, and 61 weeks post-randomization; (2) compare health utility scores (derived from SF-12) and other patient-reported outcomes among patients randomized to receive PDT + Fitbit vs. Fitbit only at 9, 21, 35, and 61 weeks post-randomization; (3) examine the relationship between engagement with PDT and clinical outcomes.

**Exploratory Aim:** Among all patients, to compare sleep and physical activity data collected within Hugo to data collected using the Fitbit (Inspire 2) at 9, 21, 35 and 61 weeks post-randomization.

## Study Duration

27 Months

## Study Design

This will be a multi-center, randomized, controlled trial of 100 patients wherein half of the patients with insomnia will receive the PEAR-003b digital therapeutic with linkage to Hugo and Fitbit (Inspire 2) and half of the patients with insomnia will not receive the PDT but will receive a Fitbit and be enrolled in Hugo. The treatment duration will be 9 weeks. All patients will be evaluated at baseline, as well as prompted to complete additional assessments at weeks 9, 21, 35, and 61 post-randomization. The PEAR-003b intervention will deliver CBT-I via mobile devices as 6 treatment core modules over 9 weeks. Additionally, we will use the Hugo platform to collect patient-generated engagement data, healthcare utilization data, and patient activity/clinical outcomes.

## Number of Study Sites

2

## Study Population

We will enroll 100 patients age between 22-64 who have been diagnosed with insomnia (50 patients will be recruited at Yale New Haven Hospital (YNHH), and 50 patients will be recruited at the Mayo

Clinic). We do not have any gender, demographic, or general health status targets; we expect to enroll the distribution of patients who receive treatment at the sleep clinic across these two systems.

**Number of Participants**

50 patients will be recruited at YNHH.

**Primary Outcome Variables**

Change in the Insomnia Severity Index (ISI) Score.

**Secondary and Exploratory Outcome Variables**

Change in: Epworth Sleepiness Score (ESS); Patient Health Questionnaire (PHQ-8); ISI, Perceived Stress Scale (PSS-10); Short-form 12 (SF-12); General Anxiety Disorder-7 scale (GAD-7); sleep outcomes, healthcare utilization outcomes, health utility scores (derived from SF-12), and relationship between engagement with PDT and clinical outcomes.

## Abbreviations

Abbreviation	Explanation
CBT-I	Cognitive-behavioral
ESS	Epworth Sleepiness Scale
GAD-7	General Anxiety Disorder-7 scale
ISI	Insomnia Severity Index
PDT	Prescription Digital Therapeutic
PHQ-8	Patient Health Questionnaire- 8
PSS-10	Perceived Stress Scale-10
SF-12	Short-form 12

## Glossary of Terms

Glossary	Explanation
CBT-I	Cognitive-behavioral therapy for insomnia (CBT-I) can effectively treat chronic insomnia
Pear-003b	Pear-003b is the PDT for insomnia that will be administered to those randomized to the treatment arm.

# 1 Introduction

## 1.1 Introductory Statement

This document is a protocol for a human research study. The purpose of this protocol is to ensure that this study is to be conducted according to ICH GCP guidelines, and according to CFR 21 Part 812, other applicable government regulations, and Institutional research policies and procedures.

## 2 Background

### 2.1.1 Device Preclinical Experience

N/A

### 2.1.2 Device Clinical Experience

In March 2020, the FDA granted authorization for PEAR-003b in treatment of patients with chronic insomnia. PEAR-003b was the first product submitted through FDA's 501(k) pathway while simultaneously reviewed as part of FDA's Software Precertification Pilot Program to help build and test FDA's Digital Health Precertification Working Model 1.0. Similar consumer digital technologies and software applications are growing in use and are increasingly brought to FDA for authorization for treatment.

The PEAR-003b digital therapeutic will be delivered via mobile devices to patients with insomnia as 6 core CBT-I modules over 9 weeks, based on the features and functionality originally tested in the SHUTi web-based program. We will also enroll patients in the Hugo platform to understand patient experience with insomnia by aggregating patients' EHR data, survey data on patient-reported outcomes, healthcare utilization metrics, and patient activity and sleep recorded via Fitbit.

### 2.2 Background/prevalence of research topic

Insomnia is one of the most prevalent health concerns and imposes a significant physical, psychological, and financial burden on patients' lives. Up to 50% of the general adult population experience insomnia symptoms, with 12-20% meeting criteria for chronic insomnia. Adults suffering from insomnia also have a higher likelihood of comorbid conditions such as depression, resulting in a reduced quality-of-life and higher rates of morbidity and mortality. The documented high rates and detrimental effects of insomnia and co-occurring disorders, provide a compelling rationale for identifying effective, accessible, easy-to-use, and cost-effective treatments.

There is empirical evidence indicating that cognitive-behavioral therapy for insomnia (CBT-I) can effectively treat chronic insomnia, with long-lasting benefits. CBT-I is now recommended as first-line therapy for insomnia. However, due to challenges associated with in-person CBT-I (e.g. lack of trained clinicians and expense, poor access, and limited fidelity), attention has turned towards use of technology to overcome obstacles and deliver CBT-I interventions (e.g., Sleep Healthy Using the Internet: SHUTi). Despite promising clinical efficacy in randomized controlled trials (RCTs), these studies have been unable to rigorously assess impact of the digital therapeutic on patient experience.

The goal of this study is to conduct a multi-center RCT to collect and evaluate real-world data from a mobile CBT-I prescription digital therapeutic (PEAR-003b) and a patient-centered data

sharing platform (Hugo). This approach will allow concurrent analysis of clinical outcomes data, healthcare utilization data, and data from connected devices. The data generated will be used alongside clinically-validated measures of insomnia to yield a multidimensional analysis of patient benefit.

## 3 Rationale/Significance

### 3.1 Problem Statement

There is empirical evidence indicating that CBT-I can effectively treat chronic insomnia. However, due to challenges associated with in-person CBT-I such as lack of trained clinicians and expense, poor access, and limited fidelity, attention has turned towards use of technology to overcome obstacles and deliver CBT-I interventions. Despite promising clinical efficacy in randomized controlled trials (RCTs), these studies have been unable to rigorously assess impact of the digital therapeutic on patient experience.

### 3.2 Purpose of Study/Potential Impact

#### Significance:

Specific Aim 1 aims to enroll patients into the Hugo data sharing platform to collect patient-reported outcome measures (PROMs) of insomnia, as well as clinically validated metrics for insomnia (all modified to a mobile-friendly format). Patient self-reported data collected via Hugo will include insomnia severity using the self-reported insomnia severity index (ISI) scale. This measure will be used to track sleep improvement progress over the 63-week study period. We will also collect data on depression (using the Patient Health Questionnaire [PHQ-8]), daytime sleepiness (measured using the Epworth sleepiness scale [ESS]), stress (measured using the perceived stress scale [PSS-10]), health-related quality of life (measured using the Short-form 12 [SF-12]) and anxiety (measured using the general anxiety disorder-7 scale [GAD-7]).

Specific Aim 2 addresses the outstanding question of whether a novel PDT (i.e., PEAR-003b) can use the Hugo platform to feasibly collect real-world healthcare utilization data from the YNHH or Mayo Clinic EHR and show trends for changes in healthcare utilization and healthy utility scores among the PDT cohort as well as the relationship between engagement with PDT and clinical outcomes. EHR data collected via the Hugo platform will include emergency department encounters, medications, inpatient visits, and outpatient visits.

We will also ask patients to link their health system data from anywhere they received care to their Hugo account. This will allow us to collect information from outside healthcare providers (i.e. if patients received care outside of YNHH or the Mayo Clinic related to their insomnia). Lastly, exploratory Aim 1 will address the feasibility of linking Fitbit (Inspire 2) to the Hugo platform in order to evaluate patient activity data including heart rate, tracking steps per day and/or exercise, sleep (total sleep time in minutes), and self-reported metrics such as weight, height and BMI.

#### Potential Impact:

Results from this study will advance our understanding of: (1) how novel ways of collecting and aggregating clinical and patient-reported outcomes data can support informed clinical decision-making (2) digital therapeutic engagement and its relationship to clinical outcomes; and (3)

evaluation of data from linked devices by providing novel information on a digital therapeutic for insomnia, connected with the Hugo platform. The outcome of this research will provide crucial data to inform the latest thinking about how data from both digital therapeutics and EHR systems can be utilized to evaluate real-world clinical and utilization outcomes. These data will be used to demonstrate the value of implementing technology within healthcare systems, supporting broad uptake of similar technology platforms. In addition, they will inform reimbursement discussions with payers to support coverage of and broad access to effective digital therapeutics.

### 3.2.1 Potential Risks

In following some intervention recommendations, participants may be asked to restrict sleep at certain times, which could lead them to initially feel more tired. This could potentially exacerbate the fatigue or sleepiness that many participants may already be experiencing. The therapeutic will direct patients to discontinue sleep restriction if they feel excessively tired.

The risk to patient privacy is no different with this study than it is with any other study that securely collects and appropriately stores personally identifiable information or protected health information. Indeed, the risk may be less since researchers are only getting access to patient data from the time of enrollment forward for 63 weeks for this study; there is no open access to the patient's entire medical record. The Hugo platform, like many other personal health records, is not a covered entity; therefore, the HIPAA privacy rule does not apply to this platform. The Hugo platform does take all necessary precautions, including industry-standard encryption, to minimize privacy and security risks to personally identifiable information stored on behalf of study participants. Hugo makes publicly available its Security Statement (<http://hugophr.com/security>), its Privacy Notice (<http://hugophr.com/privacy-notice>), and Terms of Service (<http://hugophr.com/terms-of-service/>)

Participants will undergo the possible inconvenience of filling out electronic patient-reported outcome measure surveys, which can take up to 60 minutes at each time point (at baseline, 9, 21, 35, and 61 weeks post-randomization). Additionally, some participants may feel uncomfortable providing data over the phone and have concerns about the confidentiality of their digital data. They may also have concerns about the legitimacy of a digital therapeutic. Patients will be provided the sleep clinic contact information in case they feel they need to seek support at enrollment in addition to the completion of each PHQ-8 questionnaire. The PHQ-8 is a validated measure for depression that was modified from the original PHQ-9 to not include a question about suicidality and has been used in prior studies.

Participants may also experience the possible inconvenience of wearing a Fitbit for extended periods of time and syncing these devices with the Hugo platform. Although the Fitbit has been deemed a 'Low-Risk Device' by the FDA and is therefore not deemed medical grade, there is the risk of inaccuracy in Heart Rate or sleep measurements. According to the Fitbit terms of

service, found at [www.fitbit.com/legal/terms-of-service](http://www.fitbit.com/legal/terms-of-service), "The accuracy of the data collected and presented through the Fitbit Service is not intended to match that of medical devices or scientific measurement devices."

### **3.2.2 Potential Benefits**

Knowledge gained from this study may improve outcomes for patients who suffer from insomnia. Also, through the Hugo platform, patients will have easy access to their medical records. Wearing a Fitbit may also give patients additional useful information regarding their health and fitness.

## 4 Study Objectives

### 4.1 Hypothesis

A PDT delivering remote based CBT for insomnia will improve patient reported outcomes, healthcare utilization/clinical outcomes, health utility scores, and sleep/physical activity for individuals with insomnia.

### 4.2 Primary Objective

The primary objective of this study is to compare patient-reported outcomes of insomnia (ISI), collected through Hugo, as well as clinically validated metrics for insomnia, among patients randomized to receive PDT + Fitbit vs. Fitbit only at 9, 21, 35, and 61 weeks post-randomization.

### 4.3 Secondary Objectives (if applicable)

[figure not shown]
The secondary objectives of this study are to: (1) compare real-world healthcare utilization/clinical data, collected through Hugo, including number of outpatient visits with primary care physicians, number of outpatient visits with specialty care, and medication refills for sleep or psychotropic medications among patients randomized to receive PDT + Fitbit vs. Fitbit only at 9, 21, 35, and 61 weeks post-randomization; (2) compare health utility scores and other patient-reported outcome measures among patients randomized to receive PDT + Fitbit vs. Fitbit only at 9, 21, 35, and 61 weeks post-randomization; (3) examine the relationship between engagement with PDT and clinical outcomes.

The exploratory aim of this study is to compare sleep and physical activity data collected within Hugo to data collected using the Fitbit (Inspire 2) at 9, 21, 35 and 61 weeks post-randomization, among all patients.

## 5 Study Design

### 5.1 General Design Description

This will be a Phase 2 multi-center, randomized, controlled trial (2 group X 5 assessment design) whereby half of the patients with insomnia will receive the PEAR-003b digital therapeutic with linkage to Fitbit and half of the patients with insomnia will not receive the PDT, however will receive linkage to Fitbit (100 patients total: 50 at each site). The treatment duration will be 9 weeks and there will be a 21-, 35-, and 61-week follow-up. All patients will be evaluated at baseline, as well as prompted to complete additional assessments at weeks 9, 21, 35, and 61 weeks post randomization. The PEAR-003b intervention will deliver CBT-I via mobile devices as 6 treatment core modules over 9 weeks. Using the Hugo platform, we will also collect patient-generated engagement data, healthcare utilization, and patient activity/clinical outcomes for patients with insomnia.

#### 5.1.1 Study Date Range and Duration

This project is expected to be completed no later than October 2022 with enrollment beginning in April 2021. Recruitment for patients is expected to take 14 weeks in each healthcare setting (i.e. YNHH and the Mayo Clinic) based on current patient volume, with follow up of each patient at 61 weeks post-randomization. As batches of patients complete the 21- and 61-week follow up

duration, we will begin to clean, review and verify the data as they are received from the Hugo platform on a rolling basis.

### 5.1.2 Number of Study Sites

Two

## 5.2 Outcome Variables

### 5.2.1 Primary Outcome Variables

The primary outcomes are a change in the ISI score from baseline to 9-weeks post randomization.

### 5.2.2 Secondary and Exploratory Outcome Variables (if applicable)

**Secondary Outcomes** (ascertained at baseline, 9-weeks, 21-weeks, 35-weeks, and 61-weeks post-randomization):

- Healthcare utilization outcomes reported in Hugo including number of outpatient visits and specialty care visits, number of medication refills for sleep and psychotropic medications), comparing PDT to control at all follow-up time points.
- Change from baseline to 21-, 35-, and 61-weeks in the ISI, comparing PDT to control.
- Change from baseline to 9-, 21-, 35-, and 61-weeks post-randomization in individual patient-reported outcomes including depressive symptoms (PHQ-8), daytime sleepiness (ESS), health status (SF-12), stress (PSS-10), and anxiety (GAD-7), comparing PDT to control.
- Change in sleep outcomes collected through sleep diaries (sleep efficiency (SE), sleep onset latency (SOL) (minutes), waking after sleep onset (WASO) (minutes), number of awakenings, sleep quality (scale score), time in bed, and total sleep time), from baseline to 9-, 21-, 35-, and 61-weeks post-randomization comparing PDT to control.
- Change in (and total) health utility scores using the SF-12 among patients randomized to receive PDT + Fitbit vs. Fitbit only at 9, 21, 35, and 61 weeks post-randomization
- Examine the relationship between engagement with PDT and clinical outcomes, particularly the sleep specific outcomes (ISI and diary-derived sleep metrics).

*Definition of sleep outcomes:*

- **Sleep efficiency (SE):** The ratio of total sleep time (TST) to time in bed (TIB).
- **Sleep onset latency (SOL):** The length of time that it takes to accomplish the transition from full wakefulness to sleep, normally to the lightest of the non-REM sleep stages.
- **Sleep quality:** One's satisfaction of the sleep experience, integrating aspects of sleep initiation, sleep maintenance, sleep quantity, and refreshment upon awakening.
- **Waking after sleep onset (WASO):** Periods of wakefulness occurring after defined sleep onset.

**Exploratory Outcomes** (ascertained at 9-weeks 21-weeks, 35-weeks, and 61-weeks post-randomization):

- Physical and sleep activity measured using Fitbit (steps per day, sleep [total sleep time in minutes], and self-reported metrics such as weight, height, and BMI) from baseline to 9-, 21-, 35-, and 61-weeks post randomization comparing PDT to control.

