#### 6.1.3 Method of Assignment/Randomization (if applicable)

Patients will be randomized 1:1 to the digital therapeutic or the control arm by the RA using a randomization algorithm via Hugo. Patients will be notified if they are randomized to the treatment arm on day 14 by the RA and will be provided with instruction on how to set up and create their Pear-003b account if randomized to the Pear-003b arm. The study will not employ blinding as patients will need to know if they are completing the treatment

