### 6.4.2 Sample Size Considerations

Analyses solving for minimum detectable effect sizes with 80% power were conducted with PASS software for only the primary outcomes (PASS 15). Because the models assume that each outcome is normally distributed, the outcome effects represent the average amount each outcome is expected to change with incremental shift in any explanatory variable. We will recruit a total of 100 participants and will randomly assign them to treatment and control arms based on a 50% probability of assignment. We also assume a 10% rate of drop-out between baseline and the end of follow-up, resulting in an effective sample size of N=80. Assuming a two-sided alpha threshold of 0.05, for the main outcome (change in ISI from baseline to 9-weeks post-randomization), and a power of 90% this sample size will allow us to detect an effect size of  $d=0.52$  which is  $\frac{1}{2}$  to  $\frac{1}{3}$  of what we have seen previously. Because this effect size is smaller than the levels demonstrated in randomized controlled trials, we are adequately powered to detect changes of interest in the main ISI outcome. We further note that this calculation is conservative because analysis may optionally draw from outcome values recorded at baseline and each follow-up time.

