For the secondary health utilities outcome, we will calculate the change in health utilities scores from baseline to 9-weeks, 21-weeks, 35-weeks and 61-weeks post randomization (as these are continuous variables) and perform a comparison between patients randomized to the intervention (PDT + Fitbit) and patients randomized to the control (Fitbit only). Health utilities scores are derived from the SF-6D algorithm as applied to the SF-12 data.

For the secondary engagement outcome, we will examine the relationship between engagement with PDT and clinical outcomes in the PDT arm at all follow up time points. Correlations between engagement and clinical outcomes will be evaluated using both Pearson's correlation coefficient and Spearman's rank correlation as follows. Change from baseline (Follow up – baseline) will be calculated for ISI, sleep diary-derived metrics of SOL and WASO, and PHQ-8, at both the end of treatment and the end of all follow-ups. These will be correlated with core completion rates, sleep diary completion rate, and the number of times the PDT is opened. In addition, clinical outcomes among those who complete all six cores of treatment will also be examined.

Lastly, the exploratory physical and sleep activity outcomes (measured using Fitbit) will again be compared from baseline to 9-weeks, 21-weeks, 35-weeks, and 61-weeks comparing PDT to control. These outcomes will be defined as: (a) number of steps per day; (b) sleep [total sleep time in minutes], and (c) self-reported metrics such as weight, height, and BMI). We will examine the change in scores between groups using a mixed model repeated measures ANOVA. Paired-sample *t* tests will be used to examine time effects within each condition if the overall interaction effect is significant.

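### Section 5.2.2 lists change and an undefined total for health utility, 6.4.3.2 analyses only change with no named test, and one baseline-adjusted SF-6D comparison would settle both

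*Combined protocol and SAP*

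**What the plan says.** Section 5.2.2 names the secondary outcome as "Change in (and total) health utility scores using the SF-12 among patients randomized to receive PDT + Fitbit vs. Fitbit only", at weeks 9, 21, 35 and 61. The other patient-reported and diary outcomes in that list are given as change only, so the addition in brackets is particular to utility.

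Section 6.4.3.2 is the only place with a utility analysis: "we will calculate the change in health utilities scores from baseline to 9-weeks, 21-weeks, 35-weeks and 61-weeks post randomization", followed by an unspecified comparison between the arms. Scores come from the SF-6D algorithm applied to the SF-12. No test or model is named for utility, although 6.4.3.2 names one for the other questionnaires, for utilisation, for the sleep diaries and for the Fitbit data.

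Elsewhere, the Synopsis objective is to "compare health utility scores (derived from SF-12) and other patient-reported outcomes" between the arms, and 4.3 says much the same. The Synopsis outcome list places utility among the change outcomes. Section 3.2, under Significance, hopes to "show trends for changes in healthcare utilization and healthy utility scores among the PDT cohort".

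**The concern.** A listed secondary outcome has no definition and no analysis. *Total* could mean the score at each follow-up week or something accumulated over time. If it means the follow-up score, the plan holds two versions of the utility outcome at each of four weeks. They differ by the chance imbalance between the arms at baseline, and either could later be presented as the planned result. The open choice of test adds to this in an unblinded trial.

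The comparison that is planned, on raw change, also leaves precision unused: baseline SF-6D is collected for everyone, and adjusting for it costs nothing.

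**Working it through.** **Inputs**

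- Two-sided alpha of 0.05, from 6.4.2 ("Assuming a two-sided alpha threshold of 0.05"). It is stated for the ISI and assumed here for utility.
- Equal allocation, from 6.1.3 ("Patients will be randomized 1:1 to the digital therapeutic or the control arm").
- Numbers per arm: 6.4.2 says "We also assume a 10% rate of drop-out between baseline and the end of follow-up", so 100 × 0.90 = 90, or 45 per arm. The same sentence gives "resulting in an effective sample size of N=80", or 40 per arm. Both were run.
- Effect size, SD and correlation for utility: not given, since 6.4.2 covers the primary outcome only. Assumed: equal SDs at baseline and follow-up, correlation r from 0.3 to 0.8, and effect d from 0.2 to 1.04 SD of the follow-up score.
- *Total* is read as the follow-up score, compared by an unadjusted t test. This is an assumption too.

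The plan states no figure for utility, so there is none to reproduce. The d = 0.52 in 6.4.2 belongs to the ISI. It is used below only as one point on the scale.

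**Step 1: no true effect, one week.** The two test statistics have correlation √((1 − r)/2), which is 0.592 at r = 0.3 and 0.316 at r = 0.8. The chance that at least one is significant is 0.05 + 0.05 − P(both):

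- r = 0.3: 0.10 − 0.012 = 0.088
- r = 0.8: 0.10 − 0.005 = 0.095

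This normal approximation does not depend on the numbers per arm. Simulation with t tests, 40,000 trials per setting and 45 per arm, gives 8.9% to 9.6%.

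**Step 2: true effect, one week.** With n per arm, the expected test statistic is d√(n/2) for the level and d√(n/2)/√(2(1 − r)) for the change. The chance that exactly one is significant, with 40 per arm and r from 0.3 to 0.8, is:

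| d | Versions disagree |
|---|---|
| 0.2 | 16–30% |
| 0.3 | 23–45% |
| 0.4 | 30–48% |
| 0.52 | 31–35% |
| 0.6 | 23–28% |
| 0.725 | 10–19% |
| 0.8 | 5–14% |
| 1.04 | 0.4–2.5% |

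With 45 per arm, the figures are 30–46% at d = 0.4 and 29–31% at d = 0.52.

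**Step 3: precision.** For common SD σ, the variance of the between-arm difference is:

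- level: 2σ²/n
- change: 2σ² × 2(1 − r)/n
- baseline-adjusted: 2σ²(1 − r²)/n, apart from one lost degree of freedom

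Adjusted relative to change is (1 − r²)/(2(1 − r)) = (1 + r)/2, which is 0.65 at r = 0.3 and 0.90 at r = 0.8. Adjusted relative to level is 1 − r², which is 0.91 and 0.36. In simulation at d = 0.4 with 45 per arm, power is about 47% for the level, 35% to 85% for the change, and 50% to 88% for the adjusted comparison. The adjusted comparison is highest at every correlation tried.

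**Step 4: why adjustment removes the choice.** Suppose follow-up = a + b × baseline + effect × arm + error. Subtracting baseline from both sides gives change = a + (b − 1) × baseline + effect × arm + error. Only the baseline coefficient moves. The treatment effect, its standard error and its p value are identical.

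**The case against.** The strongest reply is that this is a small wording gap in one unpowered secondary outcome. Every place that lists or analyses utility includes change. Deleting or defining one word and naming a test would resolve it, and a between-arm comparison of change is valid under randomisation. Much of that stands: the change comparison is unbiased, and the outcome is secondary. Calling the choice of adjustment a matter of taste does not stand, because with equal SDs the adjusted estimate is never less precise than either alternative beyond one degree of freedom, and it makes the choice between level and change irrelevant.

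It is also fair that the figures in Steps 1 and 2 rest on a guess about *total*. If a cumulative score was meant, they do not describe the plan's two versions.

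A reader might be tempted to infer more in four ways, and the documents do not bear these out:

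- **That the plan holds four conflicting definitions.** The objectives in the Synopsis and 4.3 are unspecific and are consistent with comparing change.
- **That an uncontrolled trend in the PDT arm will be reported as an effect.** The Aim 2 wording is significance narrative. The objectives, 5.2.2 and 6.4.3.2 all compare the arms, and no within-arm utility trend analysis is planned.
- **That the two versions disagree in some fixed share of trials with a real effect.** The share depends on the assumed effect, as Step 2 shows.
- **That the utility result is meant for payers.** Section 3.2 says only that the study's data in general will inform reimbursement discussions, and 6.4.3.6 marks health economic evaluation as not applicable.

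**Conclusion.** The mismatch between 5.2.2 and 6.4.3.2 is real: an undefined total with no analysis, and a change comparison with no named test. If *total* is the follow-up score, and either version could be claimed, the false-positive rate at one week is about 9% rather than 5% for correlations of 0.3 to 0.8. The disagreement rate under a real effect runs from under 1% to about 48% over effects of 0.2 to 1.04 SD, so no single figure should be quoted. The firmest gain is in precision: baseline adjustment brings the variance to 65–90% of that of the planned change comparison, given equal SDs and the assumed correlations. This is a free improvement to a secondary outcome. It does not affect the primary analysis.

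**What to change.** In 5.2.2 and 6.4.3.2, state one utility analysis: the between-arm difference in SF-6D score at each follow-up week, adjusted for baseline SF-6D, from the mixed model that 6.4.3.2 already specifies for the other questionnaires (unstructured covariance, Satterthwaite degrees of freedom). Baseline should enter as a covariate. If it enters as a further response with its own mean in each arm, the model returns to a comparison of change. Delete the bracketed total from 5.2.2. No cumulative endpoint is needed in its place, since that would add a second reportable utility result. Four weekly contrasts remain under this fix, so it removes the choice of version and not the choice of week.

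Bringing the Aim 2 sentence in 3.2 into line with the between-arm comparison is editorial only. The cost is a few lines of protocol text; no new data are needed.
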